6.1 Risk assessment

A Study Risk Assessment has been completed to identify the potential hazards associated with the study and to assess the likelihood of those hazards occurring and resulting in harm. This risk assessment includes:

- The known and potential risks and benefits to participants
- How high the risk is compared to normal standard practice
- How the risk will be minimised/managed

This study has been categorised as a low risk, where the level of risk is comparable to the risk of standard care. A copy of the study risk assessment may be requested from the Study Manager. The study risk assessment is used to determine the intensity and focus of monitoring activity.

7 Site and Investigator selection

This study will be carried out at 12 participating sites within the UK. Occasionally during the study, amendments may be made to the study documentation. The Study manager will issue the site with the latest version of the documents as soon as they become available. It is the responsibility of the Study Manager and CI to ensure that they obtain local relevant approval for the new documents.

8 Participant selection

Participants are eligible for the study if they meet all of the following inclusion criteria and none of the exclusion criteria apply. All queries about participant eligibility should be directed to the Study Manager before randomisation/registration.

8.1 Inclusion criteria

The study population will consist of children with ID attending SEND schools in years 5-6 (ages 9-11).

Inclusion criteria for SEND schools:

• The SEND schools to be included in this feasibility study must have firm commitment to the research and have agreed to be randomly allocated to either the intervention or the UP arm (either delayed or no access to ZF SEND) of the study.

- They should have pupils with ID and be able to identify two teachers who consent to taking part and who are willing to deliver the ZF SEND intervention over one academic year to a group of children with ID.
- The teachers must also be willing to complete a 1-day training session, to receive supervision from Partnership for Children and to complete the study records, be video recorded and participate in a qualitative interview post intervention.
- Where teachers consent to participating in the study but not to having ZF SEND sessions video-recorded, alternative ways to assess fidelity will be explored, e.g. self-report or through a member of the research team observing sessions with the head teacher's and teacher's consent.
- The schools which host ZF SEND must have the resources to support the study and must be willing to free up the teachers for training and supervision.

Inclusion criteria for child research participants:

- Administratively defined with ID (learning disability/difficulty in UK services terminology) by virtue of attending a SEND school/unit in England or Scotland.
- Schools will identify prior to randomisation at least one class of children in the age range 9-11 years to receive intervention.
- A member of the research team will initially discuss the study and inclusion criteria with teachers from the SEND schools. They will describe the communication skills required of the children to participate in the study and provide some examples of tasks similar to those used in the ZF intervention and measures to check that potential child participants are likely to have the cognitive and communication skills required to give informed consent, engage with the intervention and complete the outcome measures.
- Teachers will be asked to introduce the intervention to their class as a whole even though some children may not have sufficient communication skills to engage and benefit from a group intervention.

Inclusion criteria for parent research participants:

- Biological, step-, adoptive parent or foster carer or adult family caregiver of the children receiving the ZF SEND intervention or allocated to the UP arm of the research.
- Having a level of English language enabling (verbal) completion of outcome measures. Note that reading skills are not required. Able to provide informed consent.

8.2 Exclusion criteria

Exclusion criteria for SEND schools:

• Delivering other manualised classroom interventions designed to address mental health, wellbeing, or emotional literacy.

Exclusion criteria for child research participants:

- No parental assent to participate in the research (although this would not exclude the child from the intervention).
- Unable to assent to the MAMS assessment or to communicate using English (and adaptations to meet their communication needs cannot be put in place in the classroom setting).

Exclusion criteria for parent research participants:

- Current child protection concerns relating to the child at the point of recruitment or the family are reported by the school to be in a state of current crisis.
- Insufficient command of the (spoken) English language to complete the outcome measures or lacking capacity to give informed consent to take part in the research.

Specific diagnoses and any comorbid conditions will be recorded but not used as a basis for inclusion/exclusion. This will include the level of ID; the presence of any identifiable genetic syndrome; any physical health, sensory or motor conditions and any behavioural, emotional or mental health conditions (including Autism Spectrum Conditions and ADHD).

9 Recruitment, Screening and registration

9.1 Participant identification

Recruitment of Schools

The initial approach for participation in the study will be to schools, through our partners NASEN, BILD or other contacts through national and local Special Educational needs forums in Scotland and England to advertise and promote the research. Our partners will also use their personal knowledge of head teachers and deputies. Schools will be provided with an information sheet describing the study including the process of randomisation to intervention or a control group. One of two different information sheets will be provided to different schools at random which describes whether they will be offered the chance to participate in the Zippy's Friends programme if they are assigned to the control group or not.

The schools will be provided with the inclusion criteria for the project and will be asked to select class groups that meet the inclusion criteria and teachers who can be trained to provide the intervention within the school. Teachers will be given information about the project, again these will differ depending on whether they are offered the intervention if assigned to the control group or not and asked if they wish to have training in delivering the Zippy's friends programme. If the teachers agree to deliver the programme the schools will then send out information and assent forms to parents on behalf of the research team asking them to **assent to** the research. If parents do not assent to their child taking part in the research then the child will not take part in any of the research processes but they will continue to receive the Zippy's Friends programme as this is considered to be a normal part of the curriculum. As part of the process evaluation, a subgroup of parents who assent to the project will be approached to take part in an interview study for the process evaluation. They will be provided with information and consent forms that relate to this aspect of the project. Children will be provided with information about the project and given the opportunity to assent to the project.

9.2 Screening logs

A screening log of schools will be kept centrally by the research team. Logs of all ineligible and eligible but not consented/not approached will be kept at each site so that any biases from differential recruitment will be detected. Logs should not contain identifiable information.

9.3 Recruitment rates

A total of 12 schools will probably be recruited, exactly when recruitment takes place will depend on the course of the COVID 19 epidemic. Each school will have on average 8 eligible pupils for the study.

9.4 Informed consent

Schools

Schools will be approached via NASEN, BILD or other contacts through national and local Special Educational Needs forums or public lists in Scotland and England. Two different information sheets will be provided to different schools at random which describes the project, process of randomisation and whether they will be offered the chance to participate in the Zippy's Friends after the research programme if they are assigned to the control group or not. Informed consent will be gained from the Head Teacher of each school that wishes to participate in the research.

Teachers

Once Head Teachers have consented to participate, they will ask members of their teaching staff to take part in the project who will also be given information about the project depending on which arm of the study they are in and asked to provide their consent. Teachers will be asked to consent to running the intervention programme, completing assessments, providing reports on teaching

sessions, having sessions observed and recorded on either paper, audio or video and being interviewed by research staff. Teachers will suggest appropriate classes to participate in the study.

Parents

To protect potential participants' (pupils' and parents') privacy, the school will disseminate information sheets, 'right to object' forms and consent forms to parents/carers on the researchers' behalf. Materials will be distributed using the schools' usual communication system. For instance, some schools will use electronic 'parent mail' and others may use paper newsletters. We will request that school uses alternative methods of contact to inform any parents/carers who do not receive information using normal communication systems. We will also ask the school to display trial information on school wide forums e.g. school bulletins to ensure that all parents/carers of KS2 children are informed about the trial and have been provided with an opportunity to complete a 'right to object' form. Potential participants will be able to keep the information sheet which will provide details of who to contact if they require further information about the research or bullying. The right of the potential participant to refuse to participate without giving reasons will be respected.

A subgroup of parents will also be invited to take part in qualitative interviews designed to support the process evaluation. They will be provided with information sheets and consent forms for this specific aspect of the study.

Parental consent for children to receive the "Zippy's Friends" programme is not required as the programme falls within usual curriculum and other institutional activities (BPS, code of human ethics 2010, p.17). Parents will be able to withdraw the collection of their child's data from the trial evaluation by completing an 'opt-out' form'. The opt-out form and accompanying parent information form will detail the aim of the project, the nature of data being collected, how it will be collected, confidentiality, the potential benefits of the research and names and contacts for future inquiries. Opt-out models are standard practice in trials of this nature, as the University is relying on its public task in the public interest to undertake this research (Article 89 of the GDPR and Schedule 2, part 6 of the Data Protection Act 2018). Opt-out forms will be provided at least 2 weeks prior to the baseline survey to allow adequate time to consider the information and be compliant with the new data protection legislation regarding transparency (compliant with GDPR and DPA18 requirements).

Children

Verbal consent and completed assent forms will be gained from all children and young people before they take part. Implicit non-consent of all participants will be tested at every opportunity. Any participant who shows verbal or non-verbal signs of not wanting to take part in the study will be given the opportunity to withdraw from the study and testing will be stopped immediately. It will be made clear to all participants that if any information is disclosed that suggests the child may be at risk of harm from others or may hurt themselves or someone else, then their class teachers and/or safeguarding leads will be informed, and safeguarding procedures undertaken if necessary, to ensure their safety. Teachers will also be notified by the researcher if a child's scores indicate that they may have significant mental health difficulties, and teachers can take appropriate action which may involve informing the child's parents if necessary.

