5.3 Primary outcomes measure(s)

The feasibility questions to be addressed in the proposed research are the following:

- 1. *Recruitment of schools/children/parents*: What are the most effective recruitment pathways to identify SEND schools? What recruitment rate for parents can be achieved? What are the characteristics of schools and families of children with ID approached, screened and recruited?
- 2. **Recruitment of schools and teachers**: Can sufficient schools and teachers be recruited to run up the ZF SEND programme over one academic year? What factors influence schools' willingness to take part in the research? Can sufficient teachers be recruited and trained?
- 3. **Acceptability of research design**: Are schools and parents willing to be randomised within the context of a RCT? Do they prefer a design with delayed access to ZF SEND in the Usual Practice arm, or will they accept Usual Practice with no access to ZF SEND? How does the offer of delayed access to ZF as part of Usual Practice influence recruitment and retention of schools and pupils?
- 4. **Fidelity of implementation**: Can teachers deliver ZF SEND with a high degree of fidelity to the programme manual? What are the key barriers/ facilitators for successful implementation of ZF SEND and how does this vary across different school contexts?
- 5. *Adherence*: What proportion of children with ID in the intervention arm schools complete the ZF SEND programme?
- 6. *Retention*: What proportion of schools, children and parents/carers are retained in the research study up to the 12-month post-randomisation follow-up?
- 7. **Usual practice**: What does usual practice consist of for the support of well-being on a class-wide curriculum basis for children with ID in special schools? How is usual practice different from the programme content of ZF SEND? Does the offer of delayed access to ZF SEND as part of Usual Practice alter what is offered as part of Usual Practice in the year following randomisation?
- 8. *Estimation of parameters needed to definitive sample size calculation:* What are the estimated standard deviation, intracluster correlation coefficient, average cluster size, and coefficient of variation of cluster size for the SDQ at 12-months post-randomisation?
- 9. *Feasibility of outcome measures*: Do children, teachers and parents complete the outcome measures for the study?

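### The protocol gives two incompatible parental-agreement rules for a child's research data: active assent in the synopsis, 8.2 and 9.1, opt-out in 9.4

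*Protocol*

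**What the plan says.** Active agreement is required in three places.

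- The child exclusion criteria in section 8.2 list "No parental assent to participate in the research (although this would not exclude the child from the intervention"). The synopsis repeats this criterion.
- Section 9.1 gives the procedure: "the schools will then send out information and assent forms to parents on behalf of the research team". Without parental assent, "the child will not take part in any of the research processes".

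Section 9.4 (Parents) states a different model.

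- On the child's data: "Parents will be able to withdraw the collection of their child's data from the trial evaluation by completing an 'opt-out' form". It defends this approach: "Opt-out models are standard practice in trials of this nature".
- On paperwork: "the school will disseminate information sheets, 'right to object' forms and consent forms to parents/carers". It does not say which form governs which part of the study. The only consent forms it ties to a specific purpose are those for the qualitative interviews.

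All these sections agree that the classroom programme itself needs no parental agreement. The conflict concerns research data only.

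Recruitment and retention are primary feasibility outcomes (synopsis). Question 1 in section 5.3 is headed as covering schools, children and parents, but the one rate it names is the parents': "What recruitment rate for parents can be achieved". Question 6 asks for the proportion of children retained. Question 8 asks for the SD, ICC and average cluster size of the SDQ at 12 months.

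**The concern.** A parent can agree, refuse or not reply. The two rules treat the first two alike and the third in opposite ways. The protocol therefore does not settle whether children of non-replying parents belong to the study population.

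Several quantities that the study exists to estimate depend on the answer: the child recruitment rate, the child retention denominator, and the cluster size, SD and ICC for teacher-reported SDQ scores. An opt-in sample would also consist only of children whose parents reply, and these may differ from the rest. An analysis plan can describe the resulting sample, but it cannot change who was enrolled. There is a conduct issue too: staff who follow 9.4 for a silent parent would enrol a child whom 8.2 excludes.

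**Working it through.** **1. Do the sections conflict?** Take an otherwise eligible child who assents.

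| Parent's response | Synopsis, 8.2, 9.1 | 9.4 |
|---|---|---|
| Agrees | included | included |
| Refuses or objects | excluded | excluded |
| No reply | excluded | included |

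The rules differ by exactly the non-repliers. Three readings might reconcile them, and none does.

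- *Opt-out covers only the programme.* Section 9.4 deals with the programme separately and applies the opt-out form to the child's trial data.
- *The consent forms cover only the parents' own questionnaires.* This is plausible but unstated, and 8.2 and 9.1 still apply the assent rule to the child's participation.
- *No assent means an active refusal.* Section 9.1 has schools send forms that ask parents to assent, so silence is not assent.

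Other sections also assume signed consent. Section 9.2 logs eligible pupils who were not consented, 10.1 bases the use of earlier data on informed consent, and 13.3 starts SAE reporting at the consent signature. None of these says which rule governs the child's data.

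**2. The plan's own precision figures (section 14.3).** Half-width = 1.96 × √(p(1−p)/n), with no allowance for clustering.

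- Retention, p = 0.75, n = 96: 1.96 × √(0.1875/96) = 8.66 points. Stated: 8.7.
- School agreement, p = 12/18, n = 18: 21.78 points. Stated: 21.8.

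Both reproduce.

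**3. Illustrative size.** Inputs from the protocol: 12 schools (14.3) with on average 8 eligible pupils each (9.3), so 12 × 8 = 96. Inputs assumed, because the protocol gives none: 40-80% of parents actively agree and 5-10% actively refuse. Child assent is needed under either rule and is not modelled, so the pupil counts are upper values.

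| | Pupils enrolled | Per school | Half-width, 75% retention |
|---|---|---|---|
| Opt-in, 40% agree | 96 × 0.40 = 38.4 | 3.2 | 13.7 |
| Opt-in, 80% agree | 96 × 0.80 = 76.8 | 6.4 | 9.7 |
| Opt-out, 10% refuse | 96 × 0.90 = 86.4 | 7.2 | 9.1 |
| Opt-out, 5% refuse | 96 × 0.95 = 91.2 | 7.6 | 8.9 |

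The non-repliers are 1 − 0.80 − 0.10 = 10% to 1 − 0.40 − 0.05 = 55% of pupils, or about 10 to 53 of 96. The child recruitment rate would be 40-80% under one rule and 90-95% under the other.

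**4. If eight per school means recruited rather than eligible.** The enrolled total is then 96 under either rule, and the difference moves to the number approached: 96/0.80 = 120 to 96/0.40 = 240 under opt-in, against 96/0.95 ≈ 102 to 96/0.90 ≈ 107 under opt-out.

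**The case against.** The wording conflict is hard to dispute. The best case on the other side concerns its consequences, and much of it stands.

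- *A reader might infer that the primary recruitment rate has no single meaning.* That goes too far. The rate named in 5.3 is the parents'. Parents are a separate participant group who must be able to give informed consent (8.1), and consent forms are sent to them (9.4). Their rate can be defined whichever rule applies to the child's data. The ambiguity lies in the child rate and what follows from it.
- *A reader might infer that schools would apply different rules, so that rates could not be pooled.* Nothing supports this. Schools pass on the research team's materials, and the only planned difference between schools is the delayed-access wording. One rule in practice, described inconsistently, is at least as likely.
- *A reader might extend the effect to all SDQ parameters.* Parent-reported SDQ exists only where a parent completes it, under either rule. The effect falls mainly on teacher- and child-reported data.
- *A reader might infer bias between arms.* Pupils are enrolled before schools are randomised (9.5.1), so the contradiction does not imply it.
- *The magnitude rests on assumed response rates.* This is correct. Whether eight per school is before or after parental agreement is also unclear: 9.3 speaks of eligible pupils, while section 6 speaks of 6-10 children recruited and 14.3 of recruiting 96.

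The study is descriptive and tests no hypothesis. That limits the harm, but in a feasibility study the recruitment and retention rates are themselves the results.

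**Conclusion.** The contradiction is real and nothing in the protocol resolves it. It is a pair of conflicting enrolment rules, not a detail left to the analysis plan. It leaves open who is enrolled, the child recruitment rate, the child retention denominator, and the cluster size, SD and ICC for teacher-reported SDQ. It leaves the parents' own recruitment rate and parent-reported measures largely intact.

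The size cannot be determined from the protocol, because it equals the share of parents who do not reply. Under the assumed rates the rules differ by about 10 to 53 of 96 pupils, and retention precision under opt-in is 1.0 to 5.0 points wider than the stated 8.7. These figures are illustrations. Confidence is high for the contradiction and low for any particular magnitude. Both precision figures in 14.3 are arithmetically correct for the numbers they assume.

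**What to change.** 1. Reconcile the synopsis, 8.2, 9.1 and 9.4 to the single parental-agreement rule that received ethical approval, for teacher- and child-reported data. The synopsis must be included, since it repeats the 8.2 exclusion.
2. State in 9.4 that the consent forms cover the parents' own participation, as distinct from the child's data.
3. Define and report two rates: (a) pupils contributing data / eligible pupils in the identified classes; (b) parents completing baseline measures / parents approached.
4. If the approved rule is opt-in, state that the target of 96 assumes the parents of all eligible pupils agree, or restate the expected number of pupils and the retention precision in 14.3.

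The cost is protocol wording and a check against the approved parent materials. No change to the design is needed.

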9.5 Registration and Randomisation

9.5.1 Randomisation

A sampling frame of potentially eligible schools will be drawn up and the order in which they will be approached will be determined (focussing on geographical areas nearest the study centres). After the order for approaching schools has been determined, schools will be allocated at random to information sheets describing a study where UP either does or does not offer delayed access to ZF SEND and approached consecutively. This randomisation process will be carried out using random permuted blocks. Following recruitment, enrolment of pupils, and baseline data collection, schools will be randomised to ZF SEND or UP using minimisation, with a random element set at 80% to maintain the integrity of the allocation process. Allocations will be balanced on the basis of school size (fewer than 100 pupils total vs 100 or more pupils - informed by special school sized reported by the DfE [35]), and study site (England/Scotland). An online password protected randomisation system will be developed and implemented by staff in the Centre for Trials Research. Randomisation will be carried out by a member of staff who will not be involved in recruitment, data collection, or analysis.

10 Withdrawal & lost to follow-up

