The nested SWAT will explore the acceptability of two different study designs. One where Usual Practice does not come with the offer of delayed access to ZF SEND, and one where it does. The aim of this SWAT will be to explore the extent to which offer of a 'waitlist' comparator influences recruitment and retention of schools and pupils and modifies what is delivered as Usual Practice during the one-year post-randomisation follow-up period. The findings from this SWAT will be used to inform the design of the subsequent large-scale effectiveness study.

Study setting/context

Twelve SEND schools will be recruited in England (8) and Scotland (4) by the research team. Recruitment will take place directly by contacting SEND schools/units in each Local Authority and through Local Authority and Head Teacher committees and meetings. We will also ask third sector organisations (especially our partner organisations NASEN and BILD) to advise on recruitment strategies. The recruitment methods draw on the successful recruitment routes from the pilot study and also the research team's experience of conducting other research in SEND schools. The intervention will be delivered in schools by the teaching staff.

Recruitment and study duration

It is anticipated that twelve schools will be recruited in the Summer term starting in April 2021 Classes will be identified within those schools and on average 6-10 children and their carers recruited into the study within six weeks of the school electing to take part. Following baseline data collection, those schools allocated to the intervention will deliver it across the 2021/2022 academic year. The study will conclude in 2023.

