14.1 Randomisation

A sampling frame of potentially eligible schools will be drawn up and the order in which they will be approached will be determined (focussing on geographical areas nearest the study centres). Following this, schools will be allocated at random to information sheets describing a study where UP either does or does not offer delayed access to ZF SEND and approached consecutively. This randomisation process will be carried out using random permuted blocks. Following recruitment, enrolment of pupils, and baseline data collection, schools will be randomised to ZF SEND or UP using minimisation, with a random element set at 80% to maintain the integrity of the allocation process. Allocations will be balanced on the basis of school size (fewer than 100 pupils total vs 100 or more pupils - informed by special school sized reported by the DfE [35]), and study site (England/Scotland). An online password protected randomisation system will be carried out by a member of staff who will not be involved in recruitment, data collection, or analysis.

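### The school inclusion criterion names both SWAT versions and is given to every school, and open promotion is not reconciled with allocating each school to one information sheet before contact

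*Protocol*

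**What the plan says.** **Allocation before contact.** Sections 6, 9.5.1 and 14.1 describe an ordered process. A frame of schools is drawn up, the order of approach is fixed, and each school is allocated to one sheet: "After the order for approaching schools has been determined, schools will be allocated at random to information sheets". Section 14.1 repeats the rule: "Following this, schools will be allocated at random to information sheets describing a study where UP either does or does not offer delayed access". Sections 9.5.1 and 14.1 add that the approach is consecutive and favours areas near the study centres. On method, 9.5.1 says: "This randomisation process will be carried out using random permuted blocks".

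**Promotion.** Section 9.1 describes the initial approach as going through partner organisations and "Special Educational needs forums in Scotland and England to advertise and promote the research", and adds partners' personal knowledge of head teachers. Section 6 (study setting) adds direct contact in each Local Authority and recruitment "through Local Authority and Head Teacher committees and meetings". Section 9.4 adds public lists.

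**What schools are shown.** Sections 9.1 and 9.4 give each school one of the two sheets at random. Section 9.1 then says: "The schools will be provided with the inclusion criteria for the project". The school criterion in 8.1, repeated in the synopsis, is that schools "have agreed to be randomly allocated to either the intervention or the UP arm (either delayed or no access to ZF SEND").

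**What depends on it.** Question 3 of section 5.3 asks how the offer of delayed access affects recruitment and retention. Section 6 makes this the SWAT's aim and says the findings will inform the later trial. Section 14.3 gives a planned precision for the share of approached schools that agree.

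**The concern.** The SWAT's recruitment comparison is informative only if each school is randomised to a sheet before it hears the offer, and then decides knowing only its own version. Two features of the text work against that.

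First, the criterion given to schools mentions both forms of usual practice. A school holding the no-access sheet learns that delayed access is offered elsewhere, and the reverse. Read literally, the criterion also asks each school to accept either form. A school that would join only because of delayed access does not then clearly meet it, and such schools are the ones that would produce a difference between the sheets.

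Second, publicity through forums and committees does not reach schools in a fixed order. A head teacher who responds to it may be off the list or out of turn. The protocol does not say when that school gets its allocation, or whether it enters the denominator of the recruitment rate.

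At stake are the answer to question 3, the SWAT finding meant to shape the later design, and the meaning of the school recruitment rate. Once a school has been told of both offers, analysis cannot undo it.

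**Working it through.** **1. The passages side by side**

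| Step | Ordered process (6, 9.5.1, 14.1) | Other text (6, 8.1, 9.1, 9.4) | Reconciled? |
|---|---|---|---|
| How a school is reached | From the frame, in fixed order | Forums, committees, partners' contacts, public lists | No |
| When the sheet is allocated | Before approach | At random, timing not given for a school that responds to promotion | No |
| What the school sees | One version | One sheet, plus criteria naming both versions | No |
| Who counts as approached | Implied: allocated schools, in turn | Not stated for schools responding to promotion | No |

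Teacher information is made version-specific in 9.1. No version-specific form of the school criteria is described.

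**2. The plan's own figure**

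Inputs from 14.3: 12 of 18 approached schools agree. Wald half-width = 1.96 × √(p(1 − p)/n).

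- p = 12/18 = 0.667, n = 18
- √(0.667 × 0.333/18) = 0.111
- 1.96 × 0.111 = 0.218, i.e. 21.8 points
- Interval 44.9% to 88.4% (88.5% if the rounded figures are added)

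This matches 14.3. The calculation is sound; the open question is what the 18 counts.

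**3. Sensitivity to the meaning of approached**

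The denominators above 18 are assumptions, since the document gives no count of schools reached by promotion. The numerator is held at 12.

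| Schools counted as approached | Rate | Half-width (points) |
|---|---|---|
| 18 (the plan) | 66.7% | 21.8 |
| 24 (assumed) | 12/24 = 50.0% | 20.0 |
| 30 (assumed) | 12/30 = 40.0% | 17.5 |
| 36 (assumed) | 12/36 = 33.3% | 15.4 |

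The table shows only that the rate depends on the definition. It does not predict what will happen.

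**4. Scale of the SWAT comparison**

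Assume the 18 schools split 9 and 9 between the sheets.

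- One school moves a version's rate by 1/9 = 11.1 points.
- Half-width for the difference, both rates at 66.7%: 1.96 × √(2 × 0.667 × 0.333/9) = 1.96 × 0.222 = 0.436, i.e. 43.6 points.

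The comparison is imprecise in any case, and a single school with unclear allocation is visible in it.

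**The case against.** A reader might infer that the recruitment rate has lost its denominator and the SWAT its separation. The document does not support that.

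- Sections 9.1 and 9.4, which describe the promotion routes, still give each school one sheet at random. No section admits a school without an allocation.
- Promotion may serve only to build the frame, or to raise awareness among schools already on it.
- Section 9.2 keeps a central screening log of schools, and 12.2 plans to examine how many were approached and how many agreed.
- Question 1 of section 5.3 asks which recruitment pathways work best, so using several is intended.
- The 9.1 sentence on the criteria follows the one on the sheets and goes on to the selection of classes and teachers. The bracket in 8.1 may be shorthand for whichever version applies, and exposure before the school decides is possible rather than shown.
- The SWAT is exploratory, and section 15.1 plans descriptive analysis without formal testing.

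Most of this stands, and it limits the point to a risk. It does not remove it. The log and the counts do not define approached, and a school that sees publicity and stays silent may never be logged. If the bracket is shorthand, the text handed to schools should say so. That promotion is confined to the frame is a reasonable guess, but 9.1 calls it the initial approach and sets no such limit. Imprecision in the SWAT does not justify showing both offers to both groups.

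**Conclusion.** The point holds as an inconsistency to be put right before schools are contacted.

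- Given out as written, the criterion discloses both SWAT conditions to every school and weakens the one-sheet-per-school contrast. Dilution is the likelier effect, but the direction is not certain: a school told that others are offered more could also become less willing to join.
- The protocol does not say when a school responding to promotion is allocated, or whether it belongs in the denominator of the 14.3 rate.

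No stated precision figure is wrong. The size of any bias cannot be derived from the document. The range of 66.7% down to 33.3% rests on assumed denominators of 18 to 36, and the 11.1-point and 43.6-point figures rest on an assumed 9 and 9 split.

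**What to change.** **Synopsis and 8.1.** Replace the bracket naming both forms of usual practice with 'as described in the information sheet given to that school', and give schools version-specific criteria.

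**Sections 6 and 9.1.** State that publicity by partners, forums and committees is version-neutral. Any school that responds is added next on the frame list and allocated by the permuted-block sequence before any study information is sent to it.

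**Section 14.3.** Define approached as all schools so allocated, and report the recruitment rate by sheet version.

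**Cost.** Protocol wording and two versions of the criteria given to schools. No change to the sample size or to the stated precision. The one small downside is that promotional material cannot mention delayed access. The change does not stop heads who meet from comparing sheets, but it removes the disclosure made by the study's own documents.
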